10.3 Pharmacokinetic Analyses

10.3.1 Plasma Concentrations during IUS Use

Plasma concentrations before insertion of the IUS, and then at Days 7 and 14, and Months 1, 3, 6, 9, 12 18, 24, 30 during IUS use will be analyzed using the Treatment PK

population. Summaries will be presented for non-obese LNG20, non-obese Mirena, obese LNG20, and total LNG20 subjects. Data listings will be provided for all subjects in the PK population.

The plasma concentrations will be summarized at each time point using descriptive statistics, including geometric means, in tabular format. Plasma concentrations over time will be plotted by treatment group. Plasma concentrations reported as below the level of quantification (BLQ) will be set to zero for the purposes of summarizing and plotting concentrations.

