4.4 Substudies Entry Criteria

4.4.1 Treatment PK Substudy

In addition to meeting all entry criteria for the primary study, subjects desiring to enter the PK substudy must meet all of the following criteria:

- be 16-35 years old at the time of enrollment in the primary study

- have signed informed consent for the PK sampling prior to collection of the blood sample on day of IUS insertion
- have venous access adequate for multiple blood draws
- have not received hormonal contraception within 7 days of enrollment

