The Sponsor intends to retain all IUSs that are removed or expelled (when possible) and analyze an appropriate sample of these systems.

The following substudies will be performed at selected sites:

- Levonorgestrel PK data will be obtained in a subset of approximately 60 subjects (20 non-obese LNG20 subjects, 20 non-obese Mirena subjects and 20 obese LNG20 subjects). LNG plasma samples will be obtained at Enrollment (pre-IUS insertion), Weeks 1 and 2, and Months 1, 3, 6, 9, 12, 18, 24, 30 or Early Discontinuation after IUS insertion (includes three extra visits at Weeks 1 and 2, and Month 9, not included in the main study). These subjects will be required to give informed consent for participation in the levonorgestrel PK subset
- A subset of 60 subjects assigned to LNG20 and completing 121 months of study treatment will have levonorgestrel samples obtained at various time points after IUS removal to characterize the LNG elimination profile. Each subject in this subset will be randomized to one time point (one extra visit) post-IUS removal (24 hours, 48 hours, 7 days or 14 days) such that fifteen subjects are randomized to each time point

- A subset of 60 women assigned to LNG20 at selected sites will have transvaginal ultrasound evaluations at enrollment (pre-IUS insertion), one year, five years and ten years (pre-IUS removal) to assess changes in endometrial thickness

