10.3.2 Pharmacokinetic Parameters during IUS Use

For each subject, PK parameters will be determined using a non-compartmental approach. The following PK parameters will be calculated: C_{ssave} (pg/mL) and $AUC_{0-\text{last}}$ (day * pg/mL). For the purpose of the non-compartmental PK analysis, all plasma concentrations below the limit of quantification (BLQ) occurring after the first measurable plasma concentration will be set to zero).

PK parameters will be summarized at each time point using descriptive statistics, including geometric means.

Additionally, analyses of the effects of race and body weight on LNG exposure and exposure-response data for the secondary endpoints of return to menses (RTM), return to fertility (RTF) and endometrial thickness (ET) will be performed.

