10.3.3 Elimination PK

PK data will be summarized at each time point using descriptive statistics, including geometric means. Plasma concentrations over the first 14 days following LNG20 removal after 121 months of use will be summarized using the Elimination PK population. For the purpose of this analysis, all plasma concentrations below the limit of quantification occurring after the first measurable plasma concentration will be set to zero.

A population PK type analysis will be also performed.

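### Setting BLQ concentrations to zero while asking for geometric means gives a zero or undefined result wherever a BLQ value occurs, and the elimination rule does not clearly cover single post-removal samples

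*SAP*

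**What the plan says.** **During use (SAP 10.3.1).** The summary instruction is: "The plasma concentrations will be summarized at each time point using descriptive statistics, including geometric means, in tabular format". The time points begin before insertion: "Plasma concentrations before insertion of the IUS, and then at Days 7 and 14, and Months 1, 3, 6, 9, 12", and continue to Month 30. BLQ values "will be set to zero for the purposes of summarizing and plotting concentrations". The geometric mean is not exempted.

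**After removal (SAP 10.3.3).** "PK data will be summarized at each time point using descriptive statistics, including geometric means". The BLQ rule there reads: "all plasma concentrations below the limit of quantification occurring after the first measurable plasma concentration will be set to zero". The section also plans population PK modelling, with no BLQ method of its own.

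**General convention (SAP 5.2.1).** For summaries, continuous values recorded only as below or above a limit are replaced by the nearest exact value for that measurement, not by zero.

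**Design.** SAP section 3 gives the treatment PK groups as "20 non-obese LNG20 subjects, 20 non-obese Mirena subjects and 20 obese LNG20 subjects". In the elimination substudy 60 women are randomized to one post-removal time each (24 hours, 48 hours, 7 days or 14 days), fifteen per time. Neither document states the LLOQ or an expected concentration.

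**The concern.** A geometric mean needs strictly positive values. Under SAP 10.3.1 and 10.3.3 a BLQ value enters the summary as zero, and the SAP does not say what happens next. The table could show 0, show a missing value, or show the geometric mean of detectable values under a label that implies all women contributed.

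The elimination data are where this matters most. Plasma levonorgestrel over the 14 days after removal is a named secondary outcome (Protocol 3.2.3), and BLQ values become more plausible as washout proceeds. Zeros make the arithmetic mean fall too fast, while dropping BLQ values makes the geometric mean fall too slowly. The two columns of one table could therefore suggest different washout rates, both for reasons of data handling.

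In addition, the elimination rule is written for serial profiles, whereas the substudy takes one post-removal sample per woman.

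**Working it through.** **1. Group sizes.** Elimination: 60 / 4 = 15 per time point, as the SAP states. Treatment PK: 20 per group, and 20 + 20 = 40 for total LNG20.

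**2. One zero.** With x1 = 0 and any other positive values:
- product form: (0 × x2 × … × x15)^(1/15) = 0;
- log form: exp[(ln 0 + ln x2 + … )/15], where ln 0 is undefined.

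This holds whatever the LLOQ.

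**3. How often a time point would contain a BLQ value.** The BLQ share p is assumed, since the documents give none. The chance of at least one BLQ value among n women is 1 − (1 − p)^n.

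| p | n = 15 | n = 20 | n = 40 |
|---|---|---|---|
| 1% | 14% | 18% | 33% |
| 5% | 54% | 64% | 87% |
| 10% | 79% | 88% | 98% |
| 20% | 96% | 99% | about 100% |

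During use, the pre-insertion sample is the most exposed. Protocol 4.4.1 requires that women "have not received hormonal contraception within 7 days of enrollment", so BLQ values are plausible there.

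**4. Size of the bias.** Assume log-normal concentrations with log-SD σ = 0.5 and a share p below the LLOQ. Let z = Φ⁻¹(p), with φ the normal density.
- Detectable-only geometric mean / true = exp[σ φ(z) / (1 − p)]
- Arithmetic mean with zeros / true = Φ(σ − z)
- Geometric mean with LLOQ/2 / true = exp[σ φ(z) + p(σz − ln 2)]

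| p | z | φ(z) | Detectable-only GM | Arithmetic mean with zeros | GM with LLOQ/2 |
|---|---|---|---|---|---|
| 10% | −1.282 | 0.1755 | exp(0.0975) = 1.10 | Φ(1.782) = 0.963 (4% low) | 0.96 |
| 20% | −0.842 | 0.2800 | exp(0.1750) = 1.19 | Φ(1.342) = 0.910 (9% low) | 0.92 |
| 50% | 0 | 0.3989 | exp(0.3989) = 1.49 | Φ(0.5) = 0.691 (31% low) | 0.86 |

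These rows correspond to a true geometric mean of exp(−σz) = 1.90, 1.52 and 1.00 times the LLOQ. At 5 times the LLOQ, p = Φ(−ln 5 / 0.5) = 0.0006, so 15 women give about a 1% chance of any BLQ value.

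**5. The elimination rule.** Within the post-removal data no woman has an earlier value, so the condition can be met only by an on-treatment sample. Protocol 6.4 schedules a Month 120 sample for 16–35 year old LNG20 women enrolled before 31 May 2011. Protocol 6.6 takes one at the discontinuation visit unless one was taken in the previous 3 months. Two readings follow:
- If that sample counts, a BLQ post-removal value becomes zero and step 2 applies.
- If it does not count, SAP 10.3.3 has no rule for the value. SAP 5.2.1 might then apply, giving a different number.

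**6. What is not affected.** SAP 10.3.2 also sets BLQ values "occurring after the first measurable plasma concentration will be set to zero", but there the zeros enter a within-woman profile. The average concentration and AUC stay positive if she has measurable values, so their geometric means can be computed.

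**The case against.** **Other summaries survive.** The geometric mean is one statistic among several. SAP 5.1 already plans medians, minimums and maximums, and zeros leave the median unchanged while fewer than half the values are BLQ. SAP 10.3.1 provides listings, and SAP 5.1 requires independent program validation and senior statistical review. This stands. It limits the damage but does not tell the validating programmer which geometric mean is correct.

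**The elimination rule may work.** A reader might infer from the one-sample design that the wording about a first measurable concentration is meaningless. The documents do not support that: most women should have a recent on-treatment sample under Protocol 6.4 or 6.6. The wording is ambiguous, not empty.

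**The profile may not be distorted.** A reader might also infer that the washout profile will be wrong. That cannot be concluded. With no LLOQ, concentrations or variability in the documents, the 50% row is a severe case, and the effect nearly disappears when levels are several times the LLOQ.

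**A specific rule normally overrides a general one.** SAP 10.3.1 may simply replace 5.2.1 for concentrations. That is a reasonable reading, but the SAP does not say so, and it does not help any post-removal value that 10.3.3 leaves uncovered.

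**Pre-insertion.** If most values there are BLQ, no rule yields a useful geometric mean. That is a reason for a display cut-off, not for keeping zero.

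**Conclusion.** The conflict is real and certain in form. Wherever SAP 10.3.1 or 10.3.3 puts a zero into a concentration summary, the required geometric mean is 0 or undefined, or covers detectable values only if software drops the zero; the arithmetic mean is biased low. SAP 5.2.1 points to a different value, and 10.3.3 leaves open whether its rule reaches a single post-removal sample.

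The size is conditional. Under a log-normal distribution with log-SD 0.5, the detectable-only geometric mean is 10% to 49% too high and the arithmetic mean 4% to 31% too low as the BLQ share goes from 10% to 50%. Both shares and spread are assumptions.

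The consequence is confined to descriptive secondary pharmacokinetics. The Pearl Index uses none of these values, and no formal testing is planned. The point is worth correcting because it changes reported numbers for a named secondary outcome, but it has no bearing on the efficacy conclusion.

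**What to change.** Amend the SAP before the relevant database cut-off, so that the rule counts as prespecified under SAP 5.1:

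- In 10.3.1 and 10.3.3, state one BLQ rule for geometric means that does not use zero: for example LLOQ/2 when few values are BLQ, or a log-normal left-censored estimate. State the LLOQ.
- Report the number and percentage BLQ at each time point. If zero is kept for arithmetic means, footnote it.
- When more than half the values at a time point are BLQ, show the median or BLQ in place of a geometric mean.
- In 10.3.3, replace the condition about a first measurable concentration with a rule that applies to every post-removal sample.
- Say in 5.2.1 that plasma concentrations follow 10.3, or align the two.

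A censored likelihood in the population PK analysis is optional; the contradiction can be resolved without it. SAP 10.3.2 need not change for this point.

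The cost is SAP text and minor programming, with no new data. The downside is small: the geometric mean then rests on a stated substitution or distributional assumption. LLOQ/2, for instance, gives 0.96, 0.92 and 0.86 of the true value at 10%, 20% and 50% BLQ in the example above, which is why it suits only low BLQ shares.

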10.3.2 Pharmacokinetic Parameters during IUS Use

For each subject, PK parameters will be determined using a non-compartmental approach. The following PK parameters will be calculated: C_{ssave} (pg/mL) and $AUC_{0-\text{last}}$ (day * pg/mL). For the purpose of the non-compartmental PK analysis, all plasma concentrations below the limit of quantification (BLQ) occurring after the first measurable plasma concentration will be set to zero).

PK parameters will be summarized at each time point using descriptive statistics, including geometric means.

Additionally, analyses of the effects of race and body weight on LNG exposure and exposure-response data for the secondary endpoints of return to menses (RTM), return to fertility (RTF) and endometrial thickness (ET) will be performed.

10.3.3 Elimination PK

PK data will be summarized at each time point using descriptive statistics, including geometric means. Plasma concentrations over the first 14 days following LNG20 removal after 121 months of use will be summarized using the Elimination PK population. For the purpose of this analysis, all plasma concentrations below the limit of quantification occurring after the first measurable plasma concentration will be set to zero.

A population PK type analysis will be also performed.

10.4 IUS Analysis Post-Removal

Analysis of an appropriate sampling of IUSs for residual LNG content that are removed or expelled during the study will be summarized and plotted as a function of time of removal/expulsion.

11. SAFETY ANALYSIS

All safety analyses will be based on the Safety population.

11.1 Pregnancy Outcomes

Pregnancy outcomes will be summarized by treatment group.

11.2 Adverse Events

Menstrual bleeding and cramping/pain for the first 24 months are recorded in a daily subject diary and not on the Adverse Events CRF (unless the event is an SAE, results in IUS removal or is not related to the IUS or menstrual condition). The subject daily diary has been designed to collect IUS and menstrual bleeding and cramping AEs following insertion of the study IUS. Menstrual bleeding or cramping/pain would only be entered onto the general AE CRF if:

- Bleeding or cramping/pain meet serious criteria; an SAE report would also have to be submitted (this exception is due to data system requirements)
- Bleeding or cramping/pain result in the IUS being removed (this exception is due to data system requirements)
- Bleeding or cramping/pain is not related to the IUS or a menstrual condition.

After 24 months, menstrual bleeding and cramping/pain are recorded on the Adverse Events CRF. Analyses of cramping/pain and bleeding are described below in section 11.6 .

All adverse event summaries will be restricted to treatment-emergent adverse events (TEAE), defined as AEs occurring during or after attempted IUS insertion and those pre-attempted IUS insertion existing medical conditions that worsened during the study up to the subject's last known IUS date of use or, for subjects who have discontinued, through 30 days after the subject's last known IUS date of use. If an AE cannot be determined as treatment-emergent, it will be counted as such.

Verbatim terms on case report forms will be mapped to preferred terms and system organ classes using the Medical Dictionary for Regulatory Activities (MedDRA) dictionary. Each adverse event summary will be displayed by treatment group. Summaries that are displayed by system organ class and preferred terms will be ordered by descending order of incidence of system organ class and preferred term within each system organ class. Summaries of the following types will be presented:

- Overall subject summary of AEs, SAEs, and deaths
- Subject incidence of TEAEs and total number of unique TEAEs by MedDRA system organ class and preferred term.
- Subject incidence of TEAEs by MedDRA system organ class, preferred term, and highest severity. At each level of subject summarization a subject is classified according to the highest severity if the subject reported one or more events. AEs with missing severity will be considered severe for this summary
- Subject incidence of TEAEs by MedDRA system organ class, preferred term, and closest relationship to IUS (Related/Not Related). At each level of subject summarization a subject is classified according to the closest relationship if the subject reported one or more events. Related will be defined as “Related”, “Probably Related”, or missing. Not related will be defined as “Unlikely Related” or “Not Related”
- Subject incidence of TEAEs by MedDRA system organ class, preferred term, and closest relationship to IUS Procedure (Related/Not Related). At each level of subject summarization a subject is classified according to the closest relationship if the subject reported one or more events. Related will be defined as “Related”, “Probably Related”, or missing. Not related will be defined as “Unlikely Related” or “Not Related”
- Subject incidence of serious TEAEs and total number of unique serious TEAEs by MedDRA system organ class and preferred term

Incidence rates will include in the denominator all subjects in the Safety Population.

Missing Severity or Relationship

Missing severity or relationship to study drug will prompt queries to be sent to the investigators to provide the information. If after query resolution, the information remains missing, the following conventions will be used in summary tables.

- An event with missing severity will be considered Severe.
- An event with missing relationship will be considered related to study drug.

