7.12.1 Adverse Event CRFs

Specific Adverse Events are recorded on different CRFs.

AEs related to bleeding or cramping/pain

- With insertion - report on the IUS Insertion Questionnaire CRF
- With removal - report on the IUS Removal Questionnaire CRF
- During IUS use
 - Months 1-24:
 - The subject's diary acts as the menstrual bleeding or cramping/pain AE CRF
 - Menstrual bleeding or cramping/pain should also be reported on the general AE CRF only if:
 - Bleeding or cramping/pain are not related to the IUS or a menstrual condition
 - Bleeding or cramping/pain meet serious criteria; an SAE report would also have to be submitted (this exception is due to data system requirements)
 - Bleeding or cramping/pain result in the IUS being removed (this exception is due to data system requirements)
 - Months 25-121
 - Starting at Month 27 (phone contact), study sites will begin to assess menstrual bleeding/cramping for the prior 3 months (from Month 25; the subject will be asked to characterize her bleeding/cramping pattern for the prior 3 months and compare to when she was not using hormonal contraception prior to study entry)
 - Menstrual bleeding or cramping/pain should also be reported on the general AE CRF if:
 - Bleeding or cramping/pain is indicated as worse in severity or frequency than when the subject was not using hormones on the Bleeding/Cramping Form (verify against Menstrual History)
 - Self-reported by the subject for any months not included in the form (e.g., subject missed last contact so no form was completed) and worse in severity or frequency than when the subject was not using hormones (verify against Menstrual History)

- Bleeding or cramping/pain meets serious criteria (see section 7.8)

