11.4 Menstrual Related Cramping/Pain

11.4.1 Up to Month 24

For the first 24 months of the study. A subject will be defined as having menstrual cramping/pain (dysmenorrhea) TEAE if:

- The subject diary question, “Check box if cramping today is worse than when not using hormones” is marked

AND

- Baseline cramping/pain or dysmenorrhea is the same or worsens from what is indicated on the Menstrual History CRF based on menstrual characteristics when not using hormonal contraception.

If cramping/pain (dysmenorrhea) TEAE is recorded on the Adverse Event CRF and not on the subject diary due to the event being an SAE, results in IUS removal or is not related to the IUS or menstrual condition, the subject will be counted as having a cramping/pain (dysmenorrhea) TEAE. Subject incidence of cramping/pain or dysmenorrhea TEAEs will be described within the overall adverse event incidence summary.

11.4.2 After Month 24

For Months 25 through 121, cramping/pain (dysmenorrhea) TEAEs will be recorded only in the Adverse Event CRF and not determined based on daily subject diary responses. During these months there will be no subject diary for menstrual changes and instead a periodic (every 3 months) form characterizing their cramping and dysmenorrhea will be used. Self-reported cramping and dysmenorrhea TEAEs will be recorded on the Adverse Event CRF.

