11.5 Menstrual Related Bleeding

11.5.1 Up to Month 24

For the first 24 months of the study a subject will be defined as having a menstrual Bleeding TEAE if:

- The subject diary question, “Check box if bleeding today is heavier than when not using hormones” is marked

AND

- Baseline bleeding that is the same or worsens from what is indicated on the Menstrual History CRF based on menstrual characteristics when not using hormonal contraception.

If a bleeding TEAE is recorded on the Adverse Event CRF and not on the subject diary due to the event being an SAE, results in IUS removal or is not related to the IUS or menstrual condition, the subject will be counted as having a bleeding TEAE. Subject incidence of bleeding TEAEs will be described within the overall adverse event incidence summary.

11.5.2 After Month 24

For Months 25 through 121, bleeding TEAEs will be recorded only in the Adverse Event CRF and not determined based on daily subject diary responses. During these months there will be no subject diary for menstrual changes and instead a periodic (every 3 months) form characterizing their bleeding will be used. Self-reported bleeding TEAEs will be recorded on the Adverse Event CRF.

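### Applied as written, the missing-value defaults in SAP 11.2 class Month 1-24 diary bleeding as Severe, and diary bleeding and cramping as procedure-related, without data

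*SAP*

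**What the plan says.** **Where the events are recorded.** For Months 1-24 the subject's diary "acts as the menstrual bleeding or cramping/pain AE CRF" (Protocol 7.12.1). Under Protocol 7.12.1 and SAP 11.2, such an event also goes on the general AE CRF only if it is serious, led to removal, or is attributed to neither the IUS nor a menstrual cause.

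**When they become TEAEs.** SAP 11.4.1 and 11.5.1 define a TEAE as a ticked worse-cramping or heavier-bleeding box together with a condition on the Menstrual History CRF. On reporting, SAP 11.4.1 says: "Subject incidence of cramping/pain or dysmenorrhea TEAEs will be described within the overall adverse event incidence summary". SAP 11.5.1 says: "Subject incidence of bleeding TEAEs will be described within the overall adverse event incidence summary".

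**How TEAEs are tabulated.** SAP 11.2 plans tables by highest severity, by closest relationship to the IUS and by closest relationship to the IUS procedure. For the severity table, "AEs with missing severity will be considered severe for this summary". The two relationship tables each define Related to include missing.

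**The general rule.** A closing paragraph of SAP 11.2 adds a query step: "Missing severity or relationship to study drug will prompt queries to be sent to the investigators to provide the information". If the value is still missing afterwards, "An event with missing severity will be considered Severe" and "An event with missing relationship will be considered related to study drug".

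**The concern.** The defaults suit a blank field on an AE CRF, where an investigator should have entered a value. A diary-defined TEAE is different: no investigator grade or causality entry is described for it, so the value is absent by design. A default meant for occasional gaps would then apply to a whole class of events.

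Bleeding change and cramping are well-known effects of this type of device (Protocol 7.1.6, 7.1.7), and the period is the first two years of use. Events after Month 24 go on the AE CRF, where Protocol 7.12.3 has the investigator grade severity. A woman's highest-severity row could therefore combine a defaulted value from the first two years with real grades from later years. The procedure-relationship table could fill with menstrual events that nobody attributed to insertion or removal.

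**Working it through.** The plan states no figure on this point, so the check follows one diary-defined TEAE through the rules.

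1. **Is it a TEAE?** Yes. SAP 11.4.1 and 11.5.1 define it as one.
2. **Do the SAP 11.2 tables exclude it?** No exemption for diary events is stated. The three tables count TEAEs without qualification.
3. **Does it carry the attributes that the tables need?** Protocol 7.12.2 and 7.12.3 make relationship and severity investigator assessments. SAP 5.3.1 describes the diary as completed by the subject, with a cramping rating (none, mild, moderate, severe) and a bleeding flow category. An early diary version offered only none, spotting or bleeding. No relationship field is described.
4. **What does each table then show?**

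| Attribute | What the diary offers | Result of the rules as written |
|---|---|---|
| Cramping severity | A mild, moderate or severe rating | Severe by default only if that rating is ignored; no rule carries it into SAP 11.2 |
| Bleeding severity | Flow category, not mapped to AE severity | Severe |
| Relationship to IUS | No field; routing to the diary implies an IUS or menstrual cause | Related, which broadly agrees with the routing |
| Relationship to IUS procedure | No field; the routing says nothing about the procedure | Related, with no supporting data |

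5. **Does the query step prevent this?** Not reliably. The severity bullet and both relationship bullets treat missing values this way without mentioning a query. The query appears only in the closing paragraph, whose relationship rule names the study drug and not the procedure. These events normally have no AE CRF entry to query, and no process is described for having an investigator grade diary days afterwards.
6. **How far does one event reach?** At each level of summary a woman is classed by her highest severity and closest relationship. One defaulted event makes her Related in the procedure table. It also makes her Severe in the severity table, unless she has an event graded life-threatening.

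**The case against.** The strongest objection is that the only destination SAP 11.4.1 and 11.5.1 name for these TEAEs is the overall incidence summary, and that SAP 11.2 refers the reader to 11.6 for the cramping and bleeding analyses. SAP 11.6.1 already reports cramping by highest severity and bleeding by greatest intensity, per cycle and per 84- and 90-day interval. On that reading no default fires, and severity in Months 1-24 is reported from data. This reading is available, and it limits the harm. It is not stated, however: naming one destination does not exclude the others, and SAP 11.2 does not exempt diary events from its other tables.

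A second objection is that the defaults are conservative and follow a query. That holds for blank AE CRF fields. It does not supply a basis for attributing menstrual events to the procedure.

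A reader might infer three stronger points that the documents do not support.

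- **Every diary event becomes Severe.** Cramping has its own rating, on the form that serves as the AE CRF for these events.
- **The number of women affected can be estimated from the 4% with heavier bleeding in Protocol 7.1.7.** That figure is a 12-month overall rating by users of the marketed system. It is not a diary-event rate, and the SAP definition adds the Menstrual History condition.
- **Diary events should be set to not related to the procedure, because insertion and removal have their own questionnaires.** Protocol 7.14 limits those forms to bleeding and pain during the procedure, whereas the diary covers the time after insertion. Ruling out a procedural cause would be as unsupported as assuming one.

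**Conclusion.** The concern holds in this form: SAP 11.2 defines TEAE tables and missing-value defaults that, applied as written, class Month 1-24 diary bleeding as Severe, and diary bleeding and cramping as procedure-related, without data. For cramping severity the result depends on whether the programmer uses the diary rating. For relationship to the IUS the default does little harm.

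The conclusion rests on diary TEAEs entering the severity and relationship tables. The SAP permits this but does not state it. The size cannot be computed, because the documents give no rate of diary-defined events. The tables are descriptive, with no formal testing (SAP 5.1), and no efficacy result is touched.

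A rule should still be fixed in advance. The SAP prevails over the protocol on analysis discrepancies (SAP 1), analyses after a database cut-off count as post hoc (SAP 5.1), and successive NDA supplements are planned (SAP 5.7). Without a rule, different data cuts could be programmed differently.

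**What to change.** In SAP 11.2, limit the missing-severity and missing-relationship defaults, both in the table bullets and in the closing paragraph, to events recorded on the AE CRF. For diary-derived TEAEs, state that:

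- cramping severity is the highest diary rating on a qualifying day;
- bleeding is shown as 'diary-reported, not graded', with its greatest flow category, consistent with SAP 11.6.1;
- relationship to the IUS is shown as Related, because of the rule that routes these events to the diary;
- relationship to the IUS procedure is shown as 'not assessed', neither Related nor Not Related.

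Alternatively, state that diary TEAEs enter only the incidence table, and footnote the severity and relationship tables to SAP 11.6.1.

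Either choice needs only SAP wording and minor programming on data already collected. The downside is an extra 'not graded / not assessed' row or a footnote.
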